	DOR, and disease control (CR + PR + SD) assessed by 
• Local RECIST v1.1;• Central RECIST v1.1; PFS measured by local and central assessments Overall Survival
Exploratory Objectives	Exploratory Endpoints
Assess the preliminary antitumor efficacy of AFM24, using iRECIST tumor response criteria	OR (CR + PR) assessed by 
• Local iRECIST• Central iRECIST DOR (CR + PR + SD) assessed by 
• Local iRECIST• Central iRECIST
Assess AFM24 pharmacodynamics	
Explore the predictive potential of biomarkers measured in blood and/or tumor tissue in response to AFM24	

ADA = antidrug antibody; AUC_{tau} = area under the concentration-time curve over the dose interval; C_{max} = maximum plasma concentration; C_{min} = minimum plasma concentration; CR = complete response; DLT = dose-limiting toxicity; DOR = duration of response; iRECIST = Response Evaluation Criteria in Solid Tumors for immunotherapy; i.v.= intravenously; MTD = maximum tolerated dose; OR = overall response; PFS = progression-free survival; PK = pharmacokinetics; PR = partial response; RP2D = recommended phase 2 dose; RECIST = Response Evaluation Criteria in Solid Tumors; SAE = serious adverse events; SD = stable disease; TEAE = treatment-emergent adverse events; T_{max} = time to C_{max}.

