9.3.5 Secondary Analyses

9.3.5.1 Phase 1 (Dose Escalation) & Phase 2a (Dose Expansion)

9.3.5.1.1 Efficacy Analyses

All efficacy analyses will be done for Investigator assessed RECIST v1.1 ([Eisenhauer et al., 2009](#); [Schwartz et al., 2016](#)), Investigator assessed iRECIST ([Seymour et al., 2017](#)), Central assessed RECIST v1.1 and Central assessed iRECIST. The local Investigator assessed RECIST is the primary endpoint for the Phase 2a.

9.3.5.1.1.1 Overall Response Rate

Overall response as defined by achieving confirmed CR and/or PR assessed by RECIST v1.1 will be presented by percentage rates and where appropriate the 95% confidence intervals (CIs). Partial or complete response needs to be confirmed with repeated assessment at least 4 weeks after the initial assessment. For changes in solid tumor size waterfall plots will be presented. For all response assessments swimmer plots will be presented. All response assessments will be listed.

9.3.5.1.1.2 Disease Control Rate at Month 3, 6, and 9

Disease control at months 3, 6, and 9, as defined by achieving CR and/or PR and/or SD assessed by RECIST v1.1 will be presented by percentage rates and where appropriate the 95% CIs. Waterfall plots will be presented.

9.3.5.1.1.3 Duration of Response

The DOR defined as time from first assessment of PR or CR to follow-on first assessment of progressive disease will be summarized by descriptive statistics including median DOR and where appropriate the respective 95% CIs. DOR will also be listed.

9.3.5.1.1.4 Progression Free Survival and Overall Survival

Time from first treatment received until disease progression or OS will be summarized by Kaplan-Meier estimates, median PFS/OS and where appropriate the respective 95% CIs. Subjects with no event will be censored at the last available tumor assessment for PFS and at the last timepoint known alive for OS.

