- o. Urinalysis parameters include glucose, protein, bilirubin, ketones, blood, pH, specific gravity (microscopic examination when indicated), FSH (to confirm post-menopausal status [Screening], and human chorionic gonadotropin (female pre-menopausal subjects [Screening] (See [APPENDIX D](#), Section [14.4](#)).
- p. Coagulation may be assessed from the hematology sample.

- q. Tumor biopsy for central analysis is required for subjects in the dose escalation phase (Phase 1) only.
- r. +1 week: The second tumor biopsy will be performed on a non-dosing day during week 3 (+1 week).
- s. CT or MRI will be done at Screening and during the last week of cycles 2, 4, 6, 8, and every 3 cycles thereafter.
- t. During pre-screening, only AEs which are related to study procedures are to be recorded. AEs occurring after signing of the Main ICF but prior to the first dose of study drug should be recorded on the Medical History eCRF page (**Note:** any SAEs which are related to study procedures and occur during pre-screening and any SAEs that occur following signing the Main ICF and prior to the first dose of study drug will still be reported using the SAE form). Please also refer to Section 8.1.3 for detailed description.
- u. Concomitant medications administered after the Safety Follow-up visit should be recorded for SAEs which are considered related to study drug.

ADA = anti-drug antibodies; C = cycle; CT = computed tomography; ctDNA = circulating tumor DNA; D = day; ECG = electrocardiogram; ECOG PS = Eastern Cooperative Oncology Group Performance Status; EGFR = epidermal growth factor receptor; EOI = end of infusion; EOT = End of Treatment visit; FSH = follicle-stimulating hormone; HIV = human immunodeficiency virus; I/E = inclusion/exclusion; ICF = informed consent form; LT-FU = long term follow-up; MRI = magnetic resonance imaging; PD = pharmacodynamics; PK = pharmacokinetics; SCR = screening; S-FU = Safety Follow-up visit.

Table 12: Schedule of Pharmacokinetic, Pharmacodynamic, Immunogenicity, and Translational Assessments for Weekly AFM24 Dosing Regimen (Without Split Dosing) - For Phase 1

Sample	SCR	Cycle 1												
		D1			D3		D7	D8	D15	D22			D24	D28
		Pre	EOI ^a	+1h EOI ^a	+48h EOI ^a	+2h	+144h EOI ^a	Pre	Pre	Pre	EOI ^a	+1h EOI ^a	+48h EOI ^a	+144h EOI ^a
PK		X	X		X	X	X	X	X	X	X	X	X	X
ADA ^b		X					X	X	X					
CD16a RO	X				X					X			X	
PD (circulating lymphocytes)		X		X	X			X	X	X		X	X	
PD (cytokines) ^c		X	X		X			X	X	X	X		X	

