7.7.2 ANALYSIS OF SECONDARY EFFICACY ENDPOINTS

Phase 1 (Dose Escalation)

Non-compartmental analysis (NCA) will be conducted using concentration time data of AFM24. In addition, a population PK analysis may be conducted. Separate PK analysis plan(s) will be created as applicable and results will be presented in separate PK report(s). Plots for individual PK concentrations will be generated. PK concentrations will be listed.

ADA results (both screening and confirmatory results as well as titer) will be summarized by visit

CONFIDENTIAL

Page 16 of 22

Statistical Analysis Plan template version 1.0 dated 27-MAR-2019

and change from baseline to worst-post-baseline. Listing of ADA data will be created. The Immunogenicity data will be summarized both for the Safety Set in Phase 1.

Overall response rate (CR + PR) and disease control rate (CR + PR + stable disease [SD]), assessed by Local RECIST v1.1 will be summarized. Best confirmed overall response will be used to define the ORR. Best response is defined as the best observed response (CR>PR>SD>PD) throughout the study. See Table 1 for rules of response confirmation. Summaries will include the count and percentages of different best confirmed overall responses, ORR and DCR for each dose level. The percentages will be based on the total number of patients in the Safety population for a given dose level.

In addition, waterfall plots for percentage change from baseline for sum of longest diameter and swimmer plots showing timing and results of RECIST 1.1 response assessments (both from the central reader and the investigator).

Phase 2 (Dose Extension)

The secondary endpoints for Phase 2a match the ones for the Phase 1. Similar analyses will be performed, but the presentation will be done by Expansion Arm rather than by dose level. Analysis of Adverse Events is described in section 7.8.2.

Waterfall and swimmer plots will also be created, similar to what is described for Phase 1, but additionally color coding the Best confirmed Overall Response.

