9. DEVIATIONS FROM ANALYSIS AS DESCRIBED IN THE PROTOCOL

Apart from the above mentioned change, the planned analyses as described in this SAP do not deviate from the description in the protocol of the analyses to be performed.

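### The SAP plans one untimed disease control rate where the protocol plans rates at months 3, 6 and 9, and it files several Phase 2a secondary endpoints as exploratory

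*SAP*

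**What the plan says.** **Disease control in the protocol.** Section 9.3.5.1.1.2, which covers both phases, plans "Disease control at months 3, 6, and 9, as defined by achieving CR and/or PR and/or SD assessed by RECIST v1.1", as percentages with 95% confidence intervals where appropriate. Table 2 in section 2.0 lists the endpoint without a time: "DOR, and disease control (CR + PR + SD) assessed by" local and central RECIST v1.1 in Phase 2a.

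**Disease control in the SAP.** Section 7.7.2 states that "disease control rate (CR + PR + stable disease [SD]), assessed by Local RECIST v1.1 will be summarized". It then says: "Summaries will include the count and percentages of different best confirmed overall responses, ORR and DCR for each dose level". It also says: "Best response is defined as the best observed response (CR>PR>SD>PD) throughout the study". No time point and no confidence interval is given for DCR. Phase 2a follows the same plan, presented by expansion arm.

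**Scan schedule.** For weekly dosing, the footnote to protocol Table 11 reads: "CT or MRI will be done at Screening and during the last week of cycles 2, 4, 6, 8, and every 3 cycles thereafter". For two-weekly dosing, the footnote to Table 16 asks for four scans 8 weeks apart after baseline, then one every 12 weeks. SAP 7.2 analyses visits as recorded on the CRF and rules out reassigning them.

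**Endpoint labels.** SAP 7.7.2 states: "The secondary endpoints for Phase 2a match the ones for the Phase 1".

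**Declared deviations.** SAP section 9 says that "the planned analyses as described in this SAP do not deviate from the description in the protocol", after excepting a change said to have been mentioned above. The SAP does not say which change that is.

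**The concern.** A programmer who follows the SAP will produce one DCR per dose level or arm and none of the three timed rates. The two quantities answer different questions. A best-response rate says whether control was seen at all; a landmark rate says how many subjects still had it at a given time. In a single-arm study the second is harder to read too generously.

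The point has some weight in this study. The protocol records that Cohorts A and C stopped for futility on response and that Cohort B stopped enrolling after 8 subjects. Its Phase 1 summary (section 1.6) gives stable disease as best response in 8 of 24 response-evaluable subjects. Disease control is therefore an efficacy measure likely to have non-zero counts, and its definition should be settled before the analysis is run.

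The sentence on matching endpoints is a second, separate problem. It would put results that the protocol calls secondary under an exploratory heading in the report.

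**Working it through.** **1. Is the landmark DCR anywhere else in the SAP?** No.
- Section 7.7.2 gives the untimed DCR.
- Section 7.7.3 repeats it for iRECIST and for central reads, and adds a Clinical Benefit Rate, which is DCR with stable disease required to last at least 24 weeks.
- The Kaplan-Meier summaries give the median, the quartiles and plots, but no rates at fixed times.
- Section 9 does not name DCR.

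**2. Where do the scans fall?** Inputs are 28-day cycles (protocol 5.2), the scan footnotes, and a month of 30.4375 days (SAP 7.7.3). With C1D1 as day 1, the last week of cycle c runs from day 28(c − 1) + 22 to day 28c:

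| Cycle | Days | Ends week |
|---|---|---|
| 2 | 50–56 | 8 |
| 4 | 106–112 | 16 |
| 6 | 162–168 | 24 |
| 8 | 218–224 | 32 |
| 11 | 302–308 | 44 |

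The landmarks against these windows:
- Month 3 = 3 × 30.4375 = day 91.3. This is 35.3 days after the cycle 2 window and 14.7 days before cycle 4.
- Month 6 = day 182.6. This is 14.6 days after cycle 6 and 35.4 days before cycle 8.
- Month 9 = day 273.9. This is 49.9 days after cycle 8 and 28.1 days before cycle 11.

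The nearest scans are therefore cycles 4, 6 and 11. The two-weekly schedule gives the same weeks: 8, 16, 24, 32 and 44.

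With 28-day months, months 3, 6 and 9 are weeks 12, 24 and 36. A scan then falls at month 6 but still not at months 3 or 9, and the scan nearest month 9 becomes cycle 8 (28 days before) rather than cycle 11 (50 days after). The protocol does not define the month for this endpoint, so the convention has to be stated.

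**3. How far apart could the figures be?** Assume exponential PFS with median m months, so the proportion progression-free at t months is exp(−ln 2 × t/m). SAP 7.7.1 confirms stable disease only with a further assessment of at least stable disease 7 or more weeks later. On scheduled scans that means the second scan, at about week 15.5 (108.5/30.4375 = 3.56 months).

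| Median PFS (assumed) | SAP DCR, about week 15.5 | Month 3 | Month 6 | Month 9 |
|---|---|---|---|---|
| 2 months | 29% | 35% | 13% | 4% |
| 4 months | 54% | 60% | 35% | 21% |

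The SAP's figure exceeds the month 6 and month 9 rates and lies a little below the month 3 rate.

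**4. Do the Phase 2a secondary endpoints match Phase 1?** Protocol Table 2 against the SAP:
- Phase 1 secondary efficacy is response, DOR and disease control, all by local RECIST v1.1.
- Phase 2a secondary efficacy is response by central RECIST v1.1, DOR and disease control by local and central RECIST v1.1, PFS by local and central assessment, and OS.
- SAP 7.7.3 handles central response and disease control, DOR, PFS and OS as exploratory, and extends that to Phase 2a. DOR is secondary in both phases in Table 2.

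**The case against.** The SAP can be defended on several grounds, and part of that defence stands.

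- **Table 2 is itself untimed.** SAP section 5 adopts protocol section 2.0 for endpoints, so the SAP follows one part of the protocol. This is true. It means the protocol must also be reconciled with itself, but it does not remove the analysis planned in 9.3.5.1.1.2.
- **The SAP may not have changed anything.** It was written for protocol version 9.0 of 03Nov2022, and the protocol to hand cites guidance dated June 2023. Whether version 9.0 had the month wording cannot be checked, so a deliberate change should not be inferred.
- **Duration is not ignored.** Confirmed stable disease needs a second assessment at least 7 weeks on. The SAP also has the Clinical Benefit Rate, Kaplan-Meier PFS, swimmer plots and listings by visit. A reader might infer that the SAP's DCR takes no account of duration, and the documents do not support that. Even so, the Clinical Benefit Rate is exploratory and speaks only to about month 6.
- **Scan timing does not make the result impossible.** A reader might infer that it does. Status at months 3 and 9 could be derived from the scans on either side (weeks 8 and 16, weeks 32 and 44) if a rule were written. The result is lost through the SAP's omission; the schedule only makes a rule necessary.
- **The SAP's DCR is not always the more favourable figure.** In the illustration it is below the month 3 rate.
- **The labels change no number.** The endpoints are all analysed, and descriptively. Only their standing in the report is affected.

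**Conclusion.** The concern holds in this form: the protocol plans DCR at three landmarks, the SAP produces one untimed rate, and no declared deviation covers the gap. The contradiction between the matching sentence in SAP 7.7.2 and protocol Table 2 is also plain and needs no assumption. Neither point touches the primary endpoint or the Simon decision rules.

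The size is illustrative only. Under the assumed exponential PFS, the SAP's DCR is more than twice the month 6 rate at a median of 2 months (29% against 13%) and about one and a half times it at 4 months (54% against 35%). The gap is wider at month 9 and slightly reversed at month 3. The documents give no PFS figure, so the true gap is unknown.

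Three readings rest on inference or convention:
- The SAP ties best confirmed response expressly only to the response rate. That DCR is built the same way follows from the shared summary and from how the Clinical Benefit Rate is defined.
- The absence of a scan at months 3 and 9 assumes that scans and months are counted from the same origin. Two-weekly scans are timed from the baseline assessment, so counting months from first dose would shift them.
- Table shells are in a separate document that was not available.

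A reader might go further and infer that the sponsor means to rely on disease control because responses were few. Nothing in the documents shows that.

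**What to change.** In SAP 7.7.2:
- Add DCR at the scheduled scans nearest the landmarks: end of cycle 4 (week 16), cycle 6 (week 24) and cycle 11 (week 44). Label the results by week, and state the month convention behind the choice (30.4375 days, as elsewhere in the SAP). Tying the rate to a scheduled scan respects the rule against visit reassignment.
- Do not use week 32 for month 9. On that convention it is not the nearest scan, and it would move the landmark to an earlier, more favourable time: 224/30.4375 = 7.4 months, or 8% instead of 4% in the illustration with median 2 months.
- Use the safety set as denominator, count subjects without a qualifying scan as not controlled, and give 95% confidence intervals.
- Keep the best-response DCR as a supplementary line, labelled as such.
- Replace the sentence on matching endpoints with the Phase 2a secondary list from protocol Table 2, and treat DOR as secondary in both phases.

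In the protocol, align 9.3.5.1.1.2 and Table 2 to the same weeks. In SAP section 9, identify any difference that remains.

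The cost is some wording and one extra table from scans already collected. The later DCR figures will be lower than the single rate now planned. At weeks 24 and 44 (5.52 and 10.12 months) the illustration gives about 15% and 3% for median 2 months, and 38% and 17% for median 4 months, against 29% and 54%.

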7.7.3 ANALYSIS OF EXPLORATORY EFFICACY ENDPOINTS

Phase 1 (Dose Escalation)

Overall response rate (CR + PR) and disease control rate (CR + PR + SD), assessed by: Local iRECIST; Central RECIST v1.1 and Central iRECIST will be summarized.

In addition, Clinical Benefit Rate will be calculated and summarized. It will be defined similarly to DCR, but additionally requiring for SD to last at least 24 weeks.

Duration of Response (DOR) will be defined as (date of first progression or death – date of first response (unconfirmed))/30.4375. Patients without response will be excluded from the analysis. Patients without progression or death will be censored at the date of the last tumor scan.

Progression-Free Survival (PFS) will be defined as (date of first progression – date of first study drug injection)/30.4375. Patients without progression or death will be censored at the date of the last tumor scan.

Overall Survival (OS) will be defined as (date of death – date of first dose)/30.4375. Patients alive at the end of study will be censored on the last date of observation. Separate analyses for DOR and PFS will be created for local and central assessments. Censoring rules for all time-to-event endpoints can be seen in the table below.

Endpoint	Situation	Date	Censored/Event
Overall Survival	A death is recorded	Date of death	Event
Overall Survival	No death is recorded	Latest available observed date	Censored
Duration of Response	A PD is observed	First date of PD	Event
Duration of Response	No PD is observed, but there is a death recorded	Date of death	Event
Duration of Response	Neither PD nor Death are observed	Date of the last Tumor scan	Censored
Duration of Response	New anti-cancer therapy is started before any event is recorded	Date of the new anti-cancer therapy	Censored
Time to Response	A Response is observed	Date of the earliest (unconfirmed) response	Event
Time to Response	No Response is observed	Date of latest tumor assessment	Censored
Progression-Free Survival	A PD is observed	First date of PD	Event
Progression-Free Survival	No PD is observed, but there is a death recorded	Date of death	Event
Progression-Free Survival	Neither PD nor Death are observed	Date of the last Tumor scan	Censored
Progression-Free Survival	New anti-cancer therapy is started before any event is recorded	Date of the new anti-cancer therapy	Censored

PD = progressive disease

CONFIDENTIAL

Page 18 of 22

Statistical Analysis Plan template version 1.0 dated 27-MAR-2019

DOR, Time to Response (TTR), PFS and OS will be analyzed using Kaplan-Meier model. Summaries will include numbers and percentages of events and censored and product limit estimates of Median and the first and third Quartiles. Kaplan-Meier plots will also be created to support the summaries.

Listings of Tumor assessment data and of DOR, TTR, PFS and OS data will be created.

Lymphocyte subset counts, including number of total and activated NK cells and macrophages, will be summarized by descriptive statistics at each visit for each dose level. Listing of Lymphocyte subset counts and NK cells will be created as a part of the laboratory listings.

Summaries of the Cytokine values by visit will be created. Cytokine values will be listed.

Post-hoc subgroup analyses may be performed, where deemed necessary.

Phase 2 (Dose Extension)

The exploratory endpoints and assessments for Phase 2a match the ones for the Phase 1. Similar analyses will be performed, but the presentation will be done by Expansion Arm rather than by dose level. PFS analyses for iRECIST-based outcomes will only be performed if deemed necessary based on the interim results.

In addition, TTR will be summarized similarly to the other survival endpoints. TTR will be defined as (date of first (unconfirmed) CR or PR – date of first study drug injection)/30.4375. Patients without response of CR or PR will be censored at the last tumor assessment date. Patients with no post-baseline tumor assessments will be excluded from the analysis. TTR analyses for iRECIST-based outcomes will only be performed if deemed necessary based on the interim results.

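### SAP 7.7.3 gives conflicting PFS and DOR rules when new anti-cancer therapy starts before an event, states no row order, and uses a therapy-start date that credits unscanned time

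*SAP*

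**What the plan says.** SAP 7.7.3 states after both the DOR and the PFS definition: "Patients without progression or death will be censored at the date of the last tumor scan". No exception is made for subjects who start another treatment. The censoring table that follows has four rows for each of the two endpoints:

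- PD observed: event at first PD.
- No PD but a death: event at death.
- "Neither PD nor Death are observed": censored at the last tumor scan.
- "New anti-cancer therapy is started before any event is recorded": censored, with the date given as "Date of the new anti-cancer therapy".

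Neither the text nor the table says in what order the rows apply. The planned outputs are Kaplan-Meier plots and summaries: "Summaries will include numbers and percentages of events and censored and product limit estimates of Median and the first and third Quartiles".

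Protocol 9.3.5.1.1.4, as supplied, has only the scan rule for PFS: "Subjects with no event will be censored at the last available tumor assessment for PFS". For DOR, protocol 9.3.5.1.1.3 defines the interval up to the "follow-on first assessment of progressive disease will be summarized by descriptive statistics" and gives no censoring date. SAP section 1 says that the SAP was written for protocol version 9.0. SAP section 9 reports no departure from the protocol other than a change it describes as mentioned above, and it does not name the new-therapy rule.

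**The concern.** A subject who stops AFM24 without PD and starts another treatment has two censoring dates under the same section. If that subject later progresses or dies, the conflict is larger: one row makes the subject an event and another makes the subject censored, so a reported event count depends on an unstated choice.

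The therapy-start date is also a weak choice in itself. Progression is established at scans, and a subject last scanned some weeks before switching has not been shown to be progression-free in between. Protocol Table 2 lists PFS and DOR as Phase 2a secondary endpoints. The study is open-label and the cohorts are small, so it is better to settle the rule before the data are summarised.

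**Working it through.** **Inputs.** Time in months is days/30.4375 (SAP 7.7.3). For the weekly regimen, Protocol 14.1, Table 11 says: "CT or MRI will be done at Screening and during the last week of cycles 2, 4, 6, 8, and every 3 cycles thereafter". With 28-day cycles this means weeks 8, 16, 24 and 32, then every 12 weeks. The q2w regimen (Protocol 14.2, Table 16) has scans every 8 weeks for four assessments, then every 12 weeks. Long-term follow-up is a phone contact every 3 months that collects subsequent therapies (Protocol 3.9 and Table 11 notes). The documents give neither the number of switchers nor the gap between last scan and switch, so the cohorts below are assumed. The plan states no PFS or DOR figure to reproduce.

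**Step 1: rows that apply.**

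| Subject who starts new therapy without an event | Rows met | Result |
|---|---|---|
| No PD or death afterwards | event-free; new-therapy | censored at last scan, or at therapy start |
| PD afterwards | PD; new-therapy | event, or censored |
| Death afterwards, no PD | death; new-therapy | event, or censored |

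The first three rows already cover every subject, so the fourth has a function only if it overrides them.

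**Step 2: direction.** Each Kaplan-Meier factor is 1 − d/n. Moving a censoring date later leaves d unchanged and leaves n the same or larger. When the last scan precedes new therapy, the therapy-start date therefore gives an estimate that is unchanged or higher at every time.

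**Step 3: one subject.**
- Last scan week 8, therapy week 10: 56/30.4375 = 1.84 against 70/30.4375 = 2.30 months.
- Credit before the next due scan: up to 56/30.4375 = 1.84 months, or 84/30.4375 = 2.76 months after the fourth scan.
- If scanning continues, the order reverses. Therapy at week 12 with a last scan at week 16 gives 84/30.4375 = 2.76 months by therapy start and 112/30.4375 = 3.68 months by the literal last-scan wording.

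**Step 4: assumed cohort, n = 15.** Five PD at week 8, two at week 16, two at week 24, three at week 32. Three subjects are last scanned at week 8 and start new therapy at week 17 without PD. In all cases S(8) = 10/15 = 0.667.
- Therapy start: S(16) = 0.667 × 8/10 = 0.533; S(24) = 0.533 × 3/5 = 0.320; S(32) = 0. Median 24 weeks (168/30.4375 = 5.52 months).
- Last scan: S(16) = 0.667 × 5/7 = 0.476; S(24) = 0.476 × 3/5 = 0.286; S(32) = 0. Median 16 weeks (3.68 months).
- Both give 12 events, first quartile 8 weeks and third quartile 32 weeks.
- With therapy at week 15, no event date lies in the gap and the two rules give identical results.

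**Step 5: event count.** Let the three switchers die at week 28. If the new-therapy row comes first, there are 12 events. If the death row comes first, there are 15: S(16) = 0.533; S(24) = 0.533 × 6/8 = 0.400; S(28) = 0.400 × 3/6 = 0.200. Median 24 weeks, third quartile 28 weeks.

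**Step 6: assumed range.** Simulated cohorts of 15 had exponential progression with a true median of 8, 12 or 16 weeks and PD dated at the next nominal scan. Switch probability was 10%, 20% or 30%, with the last scan drawn at random from those before PD and no deaths. There were 4000 runs per setting. Gaps under 8 weeks changed no quartile. With gaps of 1 to 16 weeks, the median differed in 0.3% to 9.6% of cohorts and the third quartile in 4.4% to 14.4%. With n = 8, the number enrolled in Cohort B, and 2000 runs per setting, the figures were 0.0% to 2.2% and 1.0% to 6.2%.

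**Step 7: no post-baseline scan.** The screening scan may be up to 28 days before first dose (Protocol 3.2). The last-scan wording then gives PFS = −28/30.4375 = −0.92 months. This comes from the general row and needs no new therapy.

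**The case against.** The strongest reply is that the intent can be read from the table. The SAP points to the table as the place for the censoring rules, the new-therapy row contains its own chronological test, and the row does nothing unless it overrides. That stands: a reader might infer that the plan cannot be programmed, and that goes too far. What remains is that the unconditional running text contradicts the row, and that precedence over the PD and death rows has to be inferred.

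A second reply is that censoring at therapy start is a deliberate choice and that one sentence on precedence would remove the conflict. It would, but the date would still credit unscanned time.

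A third is that the numbers depend on long gaps. This is correct. Gaps under one scan interval change no quartile unless a death or off-schedule PD falls inside, and smaller cohorts show fewer changes. DOR has little practical weight, since Cohorts A and C did not meet their response criteria for continuation.

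A reader might also infer that the SAP departs from the protocol without declaring it. The documents do not establish that. The SAP was written for version 9.0, which is not available here, and the supplied protocol is silent on new therapy, so the SAP may only be adding detail.

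**Conclusion.** The point holds. SAP 7.7.3 contains two rules for the same subjects, and its most specific rule uses a date not supported by a tumor assessment. The effect is probably small: PFS and DOR are reported descriptively, and ORR and the Simon decisions do not depend on them. A change in median such as 24 against 16 weeks needs several switchers whose gaps span a scan date at which others progress. That rests on assumed cohorts, not trial data. Nor does the therapy-start date always flatter the result: where scans continue after the switch, the literal last-scan wording gives the later date. The effect on event counts arises only if PD or death is recorded after a switch. The negative-PFS case is a separate defect of the last-scan wording.

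**What to change.** 1. In the PFS and DOR new-therapy rows, censor at the last tumor assessment on or before the start of new therapy, and add the same exception to the running text after each definition.
2. State that the new-therapy row takes precedence over the PD, death and event-free rows.
3. Separately, in both the general and the new-therapy PFS rows, censor subjects with no post-baseline scan and no event at the first-dose date, so that PFS cannot be negative.

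Optional: a PFS sensitivity run counting PD or death regardless of new therapy, because censoring at a switch can be informative; and a line in SAP section 9 if the governing protocol version has no new-therapy rule.

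The cost is a few table cells, one phrase in the text and one sentence on order, plus one extra run if the sensitivity analysis is taken up. PFS and DOR estimates may be slightly less favourable than with the therapy-start date.

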3.4 STUDY TREATMENT

All doses of AFM24 will be administered as an i.v. infusion. During the dose escalation phase (Phase 1), subjects will receive AFM24 as a weekly infusion. Additional dosing regimen (ie, every 2 weeks) may be explored in the dose expansion phase (Phase 2a) only. Patients may receive AFM24 as long as they continue to show clinical benefit, as judged by the Investigator, or until disease progression, other treatment discontinuation criteria are met, or withdrawal of consent. Refer to the Pharmacy Manual for full details regarding study drug administration.

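### Kaplan-Meier for exploratory time to response, with every non-responder censored at the last scan, can overstate the probability of response

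*SAP*

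**What the plan says.** SAP 7.7.3 groups TTR with the other time-to-event endpoints: "DOR, Time to Response (TTR), PFS and OS will be analyzed using Kaplan-Meier model". The outputs include "product limit estimates of Median and the first and third Quartiles" and Kaplan-Meier plots. The event is the first unconfirmed response: "TTR will be defined as (date of first (unconfirmed) CR or PR – date of first study drug injection)/30.4375".

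Non-responders are handled by one sentence, "Patients without response of CR or PR will be censored at the last tumor assessment date", and by one line of the censoring table, which gives the censoring date as "Date of latest tumor assessment". In that table PFS and duration of response each have separate lines for progression, death and new anticancer therapy. TTR has only two lines, response observed or not observed, so progressors, deaths and patients who switch therapy all fall under censoring. The section adds: "Patients with no post-baseline tumor assessments will be excluded from the analysis".

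SAP 3.4 has patients treated while they benefit or "until disease progression, other treatment discontinuation criteria are met, or withdrawal of consent". Neither document plans a competing-risk analysis of TTR or a summary restricted to responders. TTR is not among the endpoints in Protocol 2.0.

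**The concern.** Kaplan-Meier assumes that a censored patient has the same later chance of the event as those still at risk. That is reasonable for a patient still on treatment at the data cut. It is not reasonable for one who has died, and seldom for one who has progressed and stopped treatment. Censoring them shifts their share of the curve onto the patients who remain, who are the ones still able to respond. The curve then estimates response in a hypothetical population in which nobody progresses or dies.

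At stake is a set of planned outputs, the TTR curve, median and quartiles, which can suggest more responders than the objective response rate (ORR) in the same report. The error, where it occurs, is in the drug's favour.

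**Working it through.** The documents state no TTR figure, so there is none to reproduce.

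**Inputs from the documents**
- Scans: "CT or MRI will be done at Screening and during the last week of cycles 2, 4, 6, 8, and every 3 cycles thereafter" (Protocol Appendix A). With 28-day cycles that is about weeks 8, 16, 24 and 32, then every 12 weeks.
- Response rates: 5% and 25% (null and alternative, Cohort A), 14% and 30% (Cohorts B and C), from Protocol 9.4.2, Table 10.

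**Assumed inputs (not in the documents)**
- Share f of responses that come after week 8: 20-40%, falling at week 16 or week 24.
- Median time to progression m in non-responders: 8-12 weeks, exponential.
- Late responders do not progress before they respond, and nobody is treated past progression.

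**Step 1: formulas.** At scan k let n_k be at risk, d_k respond and c_k progress and be censored, so n_(k+1) = n_k − d_k − c_k.
- SAP rule: 1-KM = 1 − Π(1 − d_k/n_k).
- Cumulative incidence with progression as a competing event: Σ d_k/N.

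The two agree until a response follows a censored progressor. From then on 1-KM is larger.

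**Step 2: two illustrative cohorts (invented counts)**
- N = 15. Scan 1: 1 response, 9 progressions. Scan 2: 1 response among the 5 left. Observed 2/15 = 13.3%. SAP rule: 1 − (14/15)(4/5) = 25.3%. A first-quartile TTR is reached although fewer than 25% responded, and 2 of 15 is within the futility region of Table 10.
- N = 41. Responses/progressions: 6/20, 4/6, 2/2. At risk: 41, 15, 5. Observed 12/41 = 29.3%. SAP rule: 1 − (35/41)(11/15)(3/5) = 62.4%. A median TTR is reached although under a third responded.

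**Step 3: expected values at week 24 for true response rate p**

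Lowest setting (f = 0.2, late responses all at week 16, m = 12): the fraction of non-responders progressed at scan 1 is 1 − 0.5^(8/12) = 0.370.
- n₂ = 1 − 0.8p − 0.370(1 − p)
- 1-KM = 1 − (1 − 0.8p)(1 − 0.2p/n₂)

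Highest setting (f = 0.4, late responses all at week 24, m = 8): the fraction progressed by the week 16 scan is 1 − 0.5^(16/8) = 0.75.
- n₃ = 1 − 0.6p − 0.75(1 − p)
- 1-KM = 1 − (1 − 0.6p)(1 − 0.4p/n₃)

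| True p | n₂ | Lowest 1-KM | n₃ | Highest 1-KM |
|---|---|---|---|---|
| 5% | 0.608 | 5.6% | 0.258 | 10.5% |
| 14% | 0.570 | 15.6% | 0.271 | 27.3% |
| 25% | 0.523 | 27.7% | 0.288 | 44.6% |
| 30% | 0.501 | 33.1% | 0.295 | 51.4% |

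Example, p = 30%, highest: 1 − 0.82 × (1 − 0.12/0.295) = 51.4%.

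With f = 0 (all responses at the first scan) both formulas return p, so the bias is zero.

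**Step 4: differences from ORR that are not due to Kaplan-Meier.** TTR counts unconfirmed responses, whereas SAP 7.7.1 requires confirmation for ORR. TTR also drops patients with no post-baseline scan, whereas ORR uses the Safety Set. Dropping them does not itself bias the Kaplan-Meier curve: censored at day 0, they would never be in a risk set at an event time, and the curve would be the same. It only makes the denominators differ.

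**The case against.** **Nothing depends on TTR.** It is exploratory, the analyses are descriptive, and the primary endpoint and Simon thresholds use counts of responders. This stands and keeps the point minor.

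**The reader is partly protected.** The same summary gives numbers and percentages of events and censored patients, TTR is listed by patient, and swimmer plots show response timing. This also stands, but the planned quartiles and plot would still be on the wrong scale.

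**Progression is not always terminal.** Protocol 4.3 and 7.2.11 allow treatment past initial radiological progression, SAP 7.7.2 takes best response over the whole study, and TTR may also be run under iRECIST. So it would be wrong to say that progressors can no longer respond. This reduces the bias but does not remove it, and death remains absolute.

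**The sizes are assumed, and the higher rates look remote.** The protocol records that Cohorts A and C stopped for futility and that Cohort B closed after 8 patients. If Table 10 was applied as written, A had at most 1 responder of 11 and C at most 2 of 15 at interim. The 25% and 30% rows are therefore unlikely to describe this study. The low-rate rows and the 15-patient example are closer to it.

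A reader might infer that the TTR curve is bound to exceed the ORR, or that the trial's efficacy conclusion is inflated. The documents support neither: the censoring bias needs a response after a censored progression or death, and the efficacy decision does not use TTR.

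**Conclusion.** The concern holds as a limited one. As written, the SAP censors patients who have progressed, died or switched therapy as if they could still respond, so 1-KM and the TTR quartiles can overstate the probability of response. Under the stated assumptions, week 24 values are about 16-27% for a true 14%, 28-45% for 25% and 33-51% for 30%. These ranges depend on response timing and progression rates that neither document gives. They shrink to no bias if every response comes at the first scan, and are smaller where treatment continues past initial progression. The mismatch from unconfirmed responses and the reduced denominator is a separate matter. The primary ORR and the futility decisions are untouched.

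**What to change.** Replace the Kaplan-Meier analysis of TTR in SAP 7.7.3 with one of these:

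- Cumulative incidence of response (Aalen-Johansen) over the Safety Set, with progression, death and new anticancer therapy as competing events. Keep censoring for patients still at risk at the data cut, and state how a patient with neither a post-baseline scan nor a competing event is counted.
- A descriptive summary of TTR (median, range) among confirmed responders only, labelled as conditional on response.

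If the first is chosen, state also whether the event is confirmed or unconfirmed response, so that the curve can be read against the ORR.

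No new data are needed: the SAP already uses progression, death and new therapy dates for PFS and duration of response. The cost is a short SAP change, a different SAS option and a curve that may look less favourable.
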